#### **Creatinine Clearance**

Estimated GFR (eGFR) by Cockcroft-Gault is collected in both central and local laboratory data. These results will be provided in data listings and will not be summarized.

Renal impairment at baseline (creatinine clearance) will be re-calculated using serum creatinine, age and weight using the Cockcroft-Gault formula.

Female 
$$CL_{cr} = \begin{bmatrix} \\ 72 \times Serum \ Creatinine \end{bmatrix} \underbrace{(140 - age) \times Body \ Weight \ (kg)}_{} \times 0.85$$

This formula expects weight to be measured in kilograms and creatinine to be measured in mg/dL; the calculated units are mL/min.

**CTCAE Grading: Hematology** 

CICAL Grading.	Trematoros			
CTCAE				
Description	Grade 1	Grade 2	Grade 3	Grade 4
Anemia, g/L	100<= AVAL <lln< td="">80<= AVAL <100	AVAL <80		</lln<>	80<= AVAL <100	AVAL <80	
Lymphocyte count decreased, 10^9/L	0.8<= AVAL <lln< td="">0.5<= AVAL < 0.8	0.2<= AVAL < 0.5	<0.2	</lln<>	0.5<= AVAL < 0.8	0.2<= AVAL < 0.5	<0.2
Lymphocyte count increased, 10^9/L		4< AVAL <=20	AVAL >20	
Neutrophil count decreased, 10^9/L	1.5<= AVAL <lln< td="">1<= AVAL <1.5	0.5<= AVAL <1	AVAL <0.5	</lln<>	1<= AVAL <1.5	0.5<= AVAL <1	AVAL <0.5
Platelet count decreased, 10^9/L	75<= AVAL <lln< td="">50<= AVAL <75	25<= AVAL <50	AVAL <25	</lln<>	50<= AVAL <75	25<= AVAL <50	AVAL <25
White blood cell decreased, 10^9/L	3.0<= AVAL <lln< td="">2.0<= AVAL <3.0	1.0<= AVAL<2.0	AVAL <1.0	</lln<>	2.0<= AVAL <3.0	1.0<= AVAL<2.0	AVAL <1.0

**CTCAE Grading: Chemistry** 

CTCAE Grading: (						
CTCAE Description	Grade 1	Grade 2	Grade 3	Grade 4		
Hypoalbuminemia,						
g/L	30<= AVAL <lln< td="">20<= AVAL <30	AVAL <20		</lln<>	20<= AVAL <30	AVAL <20			
		If baseline is n				
	ULN< AVAL	2.5xULN< AVAL	5xULN< AVAL	AVAL		
	<=2.5xULN	<=5xULN	<=20xULN	>20xULN		
		If baseline is ab		T		
Alkaline phosphatase	$2xBASE \le AVAL$	2.5xBASE< AVAL	5xBASE< AVAL			
increased, U/L	<=2.5xBASE	<=5xBASE	<= 20xBASE	>20xBASE		
		If baseline is n	ormal:	1		
	ULN< AVAL	3xULN< AVAL	5xULN< AVAL	AVAL		
	<=3xULN	<=5xULN	<=20xULN	>20xULN		
		If baseline is ab	normal:			
Alanine						
aminotransferase	$2xBASE \le AVAL$	2.5xBASE< AVAL	5xBASE< AVAL			
increased, U/L	<=2.5xBASE	<=5xBASE	<=20xBASE	>20xBASE		
		If baseline is n	ormal:	1		
	ULN< AVAL	3xULN< AVAL	5xULN< AVAL	AVAL		
	<=3xULN	<=5xULN	<=20xULN	>20xULN		
	JAOLIV	If baseline is ab		ZUKULIV		
Aspartate		Ti cuscime is as	Horman.			
aminotransferase	1.5xBASE<= AVAL	3xBASE< AVAL	5xBASE< AVAL			
increased, U/L	<=3xBASE	<=5xBASE	<=20xBASE	>20xBASE		
		If baseline is n	ormal:			
	ULN< AVAL	1.5xULN< AVAL	3xULN< AVAL	AVAL		
	<=1.5xULN	<=3xULN	<=10xULN	>10xULN		
	If baseline is abnormal:					
Blood bilirubin	BASE<= AVAL	1.5xBASE< AVAL	3xBASE< AVAL			
increased, umol/L	<=1.5xBASE	<=3xBASE	<=10xBASE	>10xBASE		
Hypocalcemia,	1101121122	, and the second	10.121152	10.151102		
mmol/L	2.0<= AVAL <lln< td="">1.75<= AVAL <2.0	1.5<= AVAL <1.75	AVAL <1.5	</lln<>	1.75<= AVAL <2.0	1.5<= AVAL <1.75	AVAL <1.5		
Hypercalcemia,						
mmol/L	ULN< AVAL <=2.9	2.9< AVAL <=3.1	3.1< AVAL <=3.4	AVAL >3.4		
Cholesterol high,			10.34< AVAL			
mmol/L	ULN< AVAL <=7.75	7.75< AVAL <=0.34	<=12.92	AVAL >12.92		
		1.5xBASE< AVAL				
		<=3xBASE;	AVAL >3xBASE;			
Creatinine increased,	ULN< AVAL	1.5xULN< AVAL	3xULN< AVAL			
umol/L	<=1.5xULN	<=3xULN	<=6xULN	AVAL >6xULN		
Hypoglycemia,	-					
mmol/L	3.0<= AVAL <lln< td=""><math>2.2 \le AVAL \le 3.0</math>	1.7<= AVAL <2.2	AVAL <1.7	</lln<>	$2.2 \le AVAL \le 3.0$	1.7<= AVAL <2.2	AVAL <1.7		
Hyperglycemia,			13.9< AVAL			
mmol/L	ULN< AVAL <=8.9	8.9< AVAL <=13.9	<=27.8	AVAL >27.8		
Hypokalemia,						
mmol/La		3.0<= AVAL <lln< td="">2.5<= AVAL <3.0	AVAL <2.5	</lln<>	2.5<= AVAL <3.0	AVAL <2.5		
Hyperkalemia,						
mmol/L	ULN< AVAL <=5.5	5.5< AVAL <=6.0	6.0< AVAL <=7.0	AVAL >7.0		
Hypomagnesemia,						
mmol/L	$0.5 \le AVAL \le LLN$	$0.4 \le AVAL \le 0.5$	$0.3 \le AVAL \le 0.4$	AVAL < 0.3		

Confidential 51 of 52

CTCAE Description	Grade 1	Grade 2	Grade 3	Grade 4
Hypermagnesemia,			1.23< AVAL	
mmol/L	ULN< AVAL <=1.23		<=3.30	AVAL >3.30
Hypophosphatemia, mmol/L	0.8<= AVAL <lln< td="">0.6<= AVAL <0.8	0.3<= AVAL <0.6	AVAL <0.3	</lln<>	0.6<= AVAL <0.8	0.3<= AVAL <0.6	AVAL <0.3
Hyponatremia, mmol/L	130<= AVAL <lln< td="">	120<= AVAL <130	AVAL <120	</lln<>		120<= AVAL <130	AVAL <120
Hypernatremia, mmol/L	ULN< AVAL <=150	150< AVAL <=155	155< AVAL <=160	AVAL >160
Hypertriglyceridemia, mmol/L	1.71<= AVAL <=3.42	3.42< AVAL <=5.7	5.7< AVAL <=11.4	AVAL >11.4

Confidential 52 of 52

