7.5.4.2 Clinical Laboratory Investigations

With the exception of urinalysis samples, all other samples collected will be analyzed by a central laboratory; a duplicate sample may be collected and analyzed by the local laboratory for immediate eligibility/ treatment decisions. If a patient has a known, clinically significant laboratory abnormality and/or associated symptoms that would require AE management or interruption of the IV study drug, either central or local laboratory tests should be analyzed prior to each administration of an IV drug infusion. The panels of laboratory tests to be performed are shown below:

Hematology: RBC and parameters (hemoglobin, hematocrit, MCV, MCH, and MCHC) and reticulocyte count, WBC and differential (with ANC), and platelet count will be assessed for all patients at screening, during treatment at each study visit, and at the Treatment Discontinuation Visit, 28-day SFU1, and at the 5-month SFU2, if toxicities are present. Hematology results must be reviewed by the investigator before the start of study drug and ongoing at times testing occurs. Additional and more frequent tests may be performed at the investigator's discretion.

Clinical Chemistry: total protein, albumin, creatinine or estimated GFR using the Cockcroft-Gault formula or institutional standard formula, BUN or urea, total bilirubin, ALP, ALT, AST, LDH, glucose, sodium, potassium, magnesium, chloride, bicarbonate (CO₂,/HCO₃-), calcium, phosphorus, TSH, Free triiodothyronine (T3; fT3); Free thyroxine (T4, fT4) at screening; TSH with reflexive fT3 and fT4 if TSH is abnormal on treatment, folic acid (first 6 cycles only), and total cholesterol will be assessed for all patients at screening, during treatment at each study visit, and at the Treatment Discontinuation Visit, 28-day SFU1, and at the 5-month SFU2, if toxicities are present. Fasting is not required before blood sampling. If pancreatitis is suspected clinically, serum lipase and amylase should be analyzed. Serum chemistry results must be reviewed by the investigator before the start of treatment with study drug and ongoing at times testing occurs.

In addition to the clinical chemistry assessments above, serology serum for hepatitis C antibody and hepatitis B surface antigen should be performed at screening. Testing for HIV must also be performed at screening if mandated locally by a given site.

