#### 11.3 Clinical Laboratory Evaluations

This study uses a central laboratory assessment of all safety lab data. Local laboratory values that are clinically relevant will be added to the case report forms. All aggregate analyses of data will be done using only the central laboratory data, but the local laboratory data will be presented in patient level data listings.

Clinical laboratory evaluations include the continuous variables for hematology, serum chemistry, and urinalysis. The laboratory values will be presented in standard units. The ontreatment period with an onset date on or after the date of first dose of study medication until the date of the last oral study medication plus 28 days or date of last IV dose plus 5 months (ie, 152 days), whichever is the latest date. Laboratory values collected during the ontreatment period will be included in the summary tables. The laboratory values collected outside of the on-treatment period will only be presented in the data listings.

For visit-based summaries; the laboratory evaluations that are during the actual scheduled cycle visit (ie, EDC visit structure) will be used, otherwise, any unscheduled laboratory evaluations that are closest to and within the same actual scheduled cycle will be used. The data sets should highlight the value for the patient that was included in the summary table, wherever feasible. The summary tables and graphs will only display data if the number of observations is greater than 10 in each treatment arm.

The summary of laboratory data will include descriptive statistics of the maximum, minimum, and last value during the on-treatment period. Summaries using descriptive statistics of the change from baseline to the maximum, minimum, and last value during the on-treatment period will also be given.

Shifts from baseline to the maximum on-treatment toxicity grade (CTCAE Version 5.0 or later) for each lab parameter will be summarized.

Figures of the mean values over time with standard error bars will be presented for key safety laboratory parameters.

Confidential 42 of 52

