#### **Grading of Central and Local Laboratory Data**

The central laboratory provides CTCAE grades according to their lab Tox Grade Report. However, in some instances the Report indicates grading is derived without the use of a baseline result where v5.0 requires use of upper limit of normal (ULN) for normal baseline and increments above baseline for abnormal baseline. Therefore, the CTCAE grading criteria will be applied in a consistent manner across all laboratory assessment using stacked data that includes both central and local results.

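### Both SAPs print an impossible Grade 2 range for high cholesterol, so values above 7.75 and up to 10.34 mmol/L have no grade as written

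*SAP*

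**What the plan says.** The chemistry grading table in COMBO SAP Appendix B grades high cholesterol in mmol/L on the analysis value. Grade 1 is "ULN< AVAL <=7.75", Grade 2 is "7.75< AVAL <=0.34", Grade 3 runs from above 10.34 to 12.92, and Grade 4 is anything above 12.92. The table in MONO SAP Appendix 2 prints the same four ranges, without repeating the unit in the row.

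Both appendices explain that the central laboratory's own grades are not simply taken over, because some were derived without using a baseline result. Instead, "the CTCAE grading criteria will be applied in a consistent manner across all laboratory assessment". COMBO SAP Section 11 summarises on-study laboratory parameters by worst grade. Section 11.3 adds, for each parameter, "Shifts from baseline to the maximum on-treatment toxicity grade". MONO SAP Section 11.2 plans the same shift tables, and Section 11.5 repeats them by subgroup.

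Cholesterol is part of the data: Protocol Section 7.5.4.2 says "total cholesterol will be assessed for all patients at screening", and again at each treatment visit, at treatment discontinuation and at the 28-day follow-up.

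**The concern.** The upper limit of the Grade 2 range is below its own lower limit, so no value can satisfy it. The adjoining cells do not close the hole: Grade 1 stops at 7.75 and Grade 3 does not begin until above 10.34.

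The table is written in terms of the analysis variable and sits beside a statement that grading will be applied uniformly to all laboratory results, so a programmer would naturally code from it. Coded literally, it would make moderate cholesterol elevation disappear from the safety tables in every arm. Protocol Section 1.1.1.2.3 names increased cholesterol among the laboratory changes seen with rucaparib, although as one of the less frequent ones. The parameter is therefore of some interest in this trial, without being a leading safety signal.

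**Working it through.** This is a check of logic; no power or sample-size formula applies.

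**Inputs** (COMBO SAP Appendix B and MONO SAP Appendix 2, high cholesterol row, mmol/L):

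| Grade | Above | Up to and including |
|---|---|---|
| 1 | ULN | 7.75 |
| 2 | 7.75 | 0.34 |
| 3 | 10.34 | 12.92 |
| 4 | 12.92 | no limit |

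Neither SAP gives a ULN for cholesterol. Values of 5.0, 5.2 and 6.2 mmol/L were assumed in turn.

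**Step 1: the Grade 2 range as printed.** A value must exceed 7.75 and be no more than 0.34. Since 0.34 < 7.75, the set is empty.

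**Step 2: what is left ungraded.** The gap lies between the top of Grade 1 and the bottom of Grade 3. It covers values above 7.75 up to and including 10.34, a width of 10.34 − 7.75 = 2.59 mmol/L. The value 7.75 itself is Grade 1.

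**Step 3: the four rules coded as printed**, over 0.00 to 20.00 mmol/L in steps of 0.01. The grid points in the gap run from 7.76 to 10.34, which is (10.34 − 7.76)/0.01 + 1 = 259 points.

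| Grade 2 upper bound | Points graded 2 | Points above ULN with no grade | Points with two grades |
|---|---|---|---|
| 0.34 (printed) | 0 | 259 (7.76 to 10.34) | 0 |
| 10.34 | 259 | 0 | 0 |

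The counts are the same for all three assumed ULNs. At the edges, with the printed bound: 7.75 is Grade 1, 7.76 and 10.34 have no grade, 10.35 is Grade 3, and 12.93 is Grade 4.

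**Step 4: what the bound should be, from the table alone.** In every other high-direction row with fixed Grade 2 and Grade 3 limits, the Grade 2 upper bound equals the Grade 3 lower bound: hypercalcemia 3.1, hyperglycemia 13.9, hyperkalemia 6.0, hypernatremia 155 and hypertriglyceridemia 5.7. The same rule gives 10.34 for cholesterol, which differs from the printed 0.34 only by a leading 1.

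**Step 5: is an unused grade intended?** Where the table leaves Grade 2 unused, the cell is blank and the neighbouring grades meet. For hypermagnesemia, Grade 1 ends and Grade 3 begins at 1.23. For hyponatremia, they meet at 130. The cholesterol cell is filled and its neighbours do not meet. The appendix note on terms graded by an older or modified CTCAE version does not list cholesterol. Nor is cholesterol among the liver tests that the appendix exempts from shift tables.

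**The case against.** The strongest reply is that nobody would be misled. Neither SAP calls the table a programming specification. Both say that CTCAE version 5.0 is used in general and list the exceptions, and cholesterol is not one of them. A programmer could therefore grade from CTCAE itself, notice the impossible range, or code cascading lower bounds, and the gap would never reach a table. This stands in part: actual misreporting is not shown, and the 0% figure holds only if the table is coded as printed. It does not remove the error. The printed range is the only cholesterol rule in either SAP, and nothing elsewhere corrects it.

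A second reply is that the fault may lie in reading the PDF, since other parts of these tables are visibly garbled. The source PDFs could not be checked. However, the same string appears in two separately issued SAPs with different layouts, and both show 10.34 intact in the next cell. A reading error is therefore unlikely.

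A third reply is that cholesterol is a secondary laboratory finding: the protocol names hemoglobin, ALT, AST and creatinine as the most common changes. That is fair, and it is why the point ranks as minor.

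**Conclusion.** The point holds. As written in both SAPs, Grade 2 high cholesterol cannot occur, and every value above 7.75 up to and including 10.34 mmol/L is ungraded, whatever the ULN (provided it is below 7.75). If the table is coded as printed, Grade 2 would be 0% in every arm. A patient whose maximum falls in the band would be shown as ungraded or at a lower grade. How many patients that affects cannot be told from the documents.

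The damage is limited to cholesterol worst-grade and shift summaries. No efficacy endpoint, alpha allocation or sample size depends on it. The conclusion assumes that the printed text matches the source PDFs.

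**What to change.** Change the Grade 2 upper bound for high cholesterol from 0.34 to 10.34 in COMBO SAP Appendix B and MONO SAP Appendix 2, so that Grade 2 covers values above 7.75 up to and including 10.34 mmol/L.

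Then check that the derived laboratory data sets contain no cholesterol value above ULN without a grade. COMBO SAP Section 3.5 records that the ATHENA-MONO primary analysis was performed on 23 March 2022. For that comparison the practical step is to confirm which bound the existing output used, and to reissue the cholesterol grade and shift tables with a short erratum if it used the printed one.

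The cost is one cell in each SAP and one data check per comparison. No clinical rule or data collection changes.

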# **APPROVAL PAGE**

# ABBREVIATIONS AND DEFINITIONS

AE	adverse event
ALP	alkaline phosphatase
ALT	alanine aminotransferase
ANCOVA	Analysis of Covariance
AST	aspartate aminotransferase
BRCA	breast cancer gene
BICR	blinded independent central review
bicrPFS	progression-free survival, blinded independent central review
BID	"Bis In Die" twice (two times) a day
BSO	bilateral salpingo-oopherectomy
CA-125	cancer antigen-125
CFI	chemotherapy-free interval
CI	confidence interval
CL cr	creatinine clearance
cm	centimeter
$C_{\min}$	trough concentration
CR	complete response
CRF	Case Report Form
CSP	clinical service provider
CSR	clinical study report
CTCAE	Common Terminology Criteria for Adverse Events
ctDNA	circulating tumor DNA
DOR	duration of response
ECG	electrocardiogram
ECOG	Eastern Cooperative Oncology Group
eCRF	electronic Case Report Form
EDC	electronic database capture
EMA	European Medicines Agency
ENGOT	European Network for Gynecological Oncological Trial groups
EQ-5D-5L	Euro-Quality of Life 5D-5L
EQ VAS	Euro-Quality of Life Visual Analog Scale
FIGO	International Federation of Gynecology and Obstetrics
FACT-O	Functional Assessment of Cancer Therapy - Ovarian
FMI	Foundation Medicine, Inc.
gBRCA	germline BRCA1/2 mutation
GCIG	Gynecologic Cancer InterGroup
GOG	Gynecologic Oncology Group
HR	hazard ratio
HRD	homologous recombination deficient
HRQoL	health-related quality of life

IDMC	Independent Data Monitoring Committee
invPFS	progression-free survival, investigator-assessed
ITT	intent-to-treat
IV	intravenous(ly)
LOH	loss of heterozygosity
LFT	liver function test
MedDRA	Medical Dictionary for Regulatory Activities
NCI-CTCAE	National Cancer Institute-Common Terminology Criteria for Adverse Events
NGS	next-generation sequencing
ORR	objective response rate
OS	overall survival
PARPi	poly (adenosine diphosphate-ribose) polymerase inhibitor
PD	progressive disease
PFS	progression-free survival
PFS2	progression-free survival on subsequent line of treatment
PK	pharmacokinetic(s)
PR	partial response
PRO	patient-reported outcome
PT	preferred term
QoL	quality of life
QT	time from beginning of the Q wave to the end of the T wave
QTc	QT interval corrected for heart rate
QTcB	QT interval corrected using Bazett's formula
QTcF	QT interval corrected using Fridericia's formula
RECIST	Response Evaluation Criteria in Solid Tumors
SAE	serious adverse event
SAP	statistical analysis plan
SD	stable disease
SFU1	Safety Follow-up Visit 1
SFU2	Safety Follow-up Visit 2
SOC	System Organ Class
tBRCA	deleterious BRCA1/2 mutation in tumor tissue
TDT	time to treatment discontinuation of oral dose
TEAE	treatment-emergent adverse event
TFST	time to first subsequent anticancer treatment
TOI	trial outcome index
TSST	time to second subsequent anticancer treatment
ULN	upper limit of normal
VAS	Visual Analog Scale
WHO	World Health Organization

**Analysis Population Definitions** 

ITT Population	All randomized patients
HRD Population	Patients with HRD + tumors (an NGS HRD assay result), composed of tBRCA and non-tBRCA LOH high
Safety Population	All patients who received at least 1 dose of protocol-specified treatment

# **HRD Subgroup Definitions**

tBRCA	Patient with deleterious BRCA1/2 mutation in tumor tissue
non-tBRCA LOH high	Patients without a tBRCA mutation and with percent of tumor genome LOH $\geq$ 16%
non-tBRCA LOHlow	Patients without a tBRCA mutation and with percent of tumor genome LOH < 16%
non-tBRCA LOH unknown	Patients without a tBRCA mutation and with percent of tumor genome LOH unknown

Clovis Oncology 10 February 2022

#### 1 INTRODUCTION

This document describes the statistical analyses and data presentations to be performed for the ATHENA monotherapy (ATHENA-MONO) treatment comparison as part of the Clinical Study Protocol: CO-338-087/GOG-3020 / ENGOT-ov45/NCRI/ATHENA (A Multicenter, Randomized, Double-blind, Placebo-controlled Phase 3 Study in Ovarian Cancer Patients Evaluating Rucaparib and Nivolumab as Maintenance Treatment Following Response to Front-ine Platinum-based Chemotherapy). ATHENA-MONO consists of the relevant endpoints pertaining to the comparison of treatment Arm B (oral rucaparib + IV placebo) versus Arm D (oral placebo + IV placebo).

This SAP provides additional details concerning the statistical analyses for ATHENA-MONO comparisons, already outlined in the original protocol (dated 02 March 2018), Protocol Amendment 1 (dated 05 July 2018), Protocol Amendment 2 (dated 26 October 2020), protocol Amendment 3 (08 September 2021), and Protocol Amendment 4 (dated 29 November 2021).

Since this study is still ongoing as of the maturity of the primary analysis for ATHENA-MONO, a visit cut-off will be applied to all data sets and fully documented in the statistical package data set documentation.

#### 2 OVERALL STUDY DESIGN, OBJECTIVES, AND ENDPOINTS

### 2.1 Study Objectives Outlined in Protocol

# Table 1 Primary, Secondary, and Exploratory Objectives for the Monotherapy Treatment Comparison

#### **Primary Objectives**

To evaluate PFS by RECIST, as assessed by the investigator (invPFS)

#### Secondary Objectives

- 1. To evaluate PFS by RECIST, as assessed by the BICR (bicrPFS)
- 2. To evaluate survival benefit
- 3. To evaluate ORR and DOR, as assessed by the investigator, in patients with measurable disease at baseline
- 4. To evaluate safety

#### **Exploratory Objectives**

- 1. To evaluate PFS2
- 2. To evaluate efficacy and safety in the tBRCA subgroup for the comparison of rucaparib vs placebo (invPFS, bicrPFS, OS, ORR, DOR, and safety)
- 3. To evaluate HRQoL as assessed by the TOI of the FACT-O
- 4. To evaluate PRO utilizing the EQ-5D-5L
- 5. To characterize PK of rucaparib as a monotherapy

## 2.2 Study Design

ATHENA is a Phase 3, randomized, double-blind, dual placebo-controlled study of rucaparib in combination with nivolumab in patients with newly diagnosed epithelial ovarian, fallopian tube, or primary peritoneal cancer who have responded to their first-line platinum-based regimen.

The study will enroll patients with high-grade epithelial ovarian, primary peritoneal, or fallopian tube cancer who completed first-line platinum-based chemotherapy and surgery with a response of either a CR or a PR, defined as RECIST v1.1 PR or a CA-125 PR by GCIG criteria to their first platinum-based regimen. Patients must have received 4 to 8 cycles of first-line platinum doublet treatment per standard clinical practice, including a minimum of 4 cycles of a platinum/ taxane combination; no other prior treatment for ovarian cancer, including maintenance treatment, is permitted. Patients need to have had completed cytoreductive surgery, including at least a BSO and partial omentectomy, either prior to chemotherapy (primary surgery) or following neoadjuvant chemotherapy (interval debulking).

Page 10 of 54

Patients will be required to provide archival tumor tissue or a screening biopsy for central laboratory analysis prior to enrollment. Genes of interest will be sequenced using Foundation Medicine's (FMI) NGS test, which examines a panel of cancer-related genes, including BRCA1/2 and the degree of tumor LOH.

The results from the NGS test will be utilized to classify patients into the following randomization stratification groups:

- tBRCA (deleterious BRCA1 or BRCA2 mutation)
- non-tBRCA LOHhigh (LOH > 16%)
- non-tBRCA LOHlow (LOH < 16%)
- non-tBRCA LOHunknown

The sponsor will remain blinded to all NGS test results (including all tBRCA results), as well as existing local BRCA testing results, until the primary efficacy analysis is conducted.

Approximately 1000 patients will be randomized in the Double-blind Treatment Phase using a 4:4:1:1 ratio into the following four treatment groups:

- Arm A: oral rucaparib + IV nivolumab (n = 400);
- Arm B: oral rucaparib + IV placebo (n = 400);
- Arm C: oral placebo + IV nivolumab (n = 100); or
- Arm D: oral placebo + IV placebo (n = 100).

The randomization is stratified by the following factors:

- HRD status (tBRCA, non-tBRCA LOHhigh, non-tBRCA LOHlow, and non-tBRCA LOHunknown);
- Disease status (no residual disease vs residual disease); and
- Timing of surgery (primary surgery vs interval debulking).

Randomization to study treatment must occur within 8 weeks following a patient's first day of the last cycle of chemotherapy.

During the Double-blind Treatment Phase (continuous 28-day treatment cycles), the double blinded oral study treatment will be administered on Day 1 of Cycle 1 and continue BID throughout the cycle as monotherapy. IV study drug administration will begin on Day 1 of Cycle 2 during the Double-blind Treatment Phase. Patients will have clinic visits on Day 1 and Day 15 of Cycles 1 and 2, and on Day 1 of every cycle thereafter. Study treatments will continue until 24 months after planned initiation of oral/ IV combination study treatment

(C2D1), disease progression, unacceptable toxicity, or withdrawal of participant consent, whichever happens first.

During the Treatment Phase patients will be monitored for safety and efficacy. Assessments will include AEs, physical examination, vital signs and weight measurement, central laboratory hematology, serum chemistry, and CA-125 measurement, concomitant medications, therapies, and procedures, ECOG performance status, disease status assessment, ctDNA analysis, study drug administration and accountability, and PRO. ECGs and urinalysis will be performed as clinically indicated. Blood samples will also be collected to determine whether any mutation identified is of germline or somatic origin.

Patients will be assessed for disease status per RECIST v1.1 every 12 calendar weeks (flexibility with scheduling within 1 week prior to planned imaging date is permitted) following initiation of oral/IV combination study treatment on Day 1 of Cycle 2 (the first scan will be 16 weeks after initiation of oral study treatment) for the first 3 years after initiation of oral/IV study treatment and every 24 weeks thereafter until objective radiological disease progression; disease status will also be assessed at discontinuation of treatment and as clinically indicated. Disease progression will only be determined by RECIST v1.1. Patients experiencing disease progression by RECIST v1.1, as assessed by the investigator, will be discontinued from treatment and enter the Follow-up Phase of the study. If the patient has met criteria for radiologic progression by RECIST, but the patient is still receiving benefit from the study drug(s) according to the investigator, then continuation of treatment will be considered for a maximum duration of 24 months after planned initiation of oral/IV combination study treatment.

All CT/MRI scans will be sent to an external vendor for BICR. However, all treatment decisions will be based on investigator assessment of scans.

After the treatment is discontinued, all patients will be followed for at least 5 months after the last dose of IV study drug treatment. There will be 2 follow-up visits: Safety Follow-up Visit 1 (SFU1) should occur 28 days (± 7 days) after last dose of the oral and/or IV study drug (whichever occurs later), and Safety Follow-up Visit 2 (SFU2) should occur approximately 5 months (± 7 days) after the last dose of IV study drug treatment. If a patient remains on oral study drug after discontinuation of IV study drug, SFU2 visit can be performed at a cycle visit, provided it has been at least 5 months since the last IV study drug dose. Patients who discontinued treatment for a reason other than disease progression or death should continue to have tumor scans performed at 12-week intervals from C2D1 for the first 3 years after initiation of oral/IV combination study drug treatment and then every 24 weeks thereafter until objective radiological disease progression by RECIST v1.1, as assessed by the investigator, is documented.

[figure not shown]
Patients will also be followed long-term for survival, subsequent treatments, disease progression (if treatment discontinuation was for reason other than disease progression or death), and monitoring for secondary malignancy every 12 weeks ( $\pm$  14 days) until death, loss to follow-up, withdrawal of consent, or study closure.

Clovis Oncology 10 February 2022

An open-label safety cohort in Japan, with patients receiving open-label oral rucaparib + IV nivolumab combination treatment, is part of the overall ATHENA study. The analyses for the open-label cohort will not be summarized in ATHENA-MONO, but it will be further detailed and summarized in the ATHENA combination treatment comparison (ATHENA-COMBO) SAP.

Figure 1 includes a study design outlining key assessments within the Screening Phase, Double-blind Randomized Treatment Phase, and lastly, the Follow-up Phase.

Figure 1 Schema of Study Design

Stratification variables:

- HRD classification
- Disease status
- Timing of Surgery

